## **9. EFFICACY EVALUATIONS**

### **9.1. Analysis of Primary Endpoints**

The primary endpoint is the proportion of patients with 1) an HbA1c  $\leq$  6.5% at Day 365, AND 2) free of severe hypoglycemic events (for definition see Section 2.7.2a) from Day 28 to Day 365, inclusive, following the first and the last islet transplant, respectively, with the day of corresponding transplant designated Day 0.

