#### **9.1.1. Analysis of Primary Endpoints**

The primary analysis is to estimate the true rate of this composite favorable outcome at one year in patients in the ITT population. The proportion of favorable outcomes will be used as the point estimate. An exact (Clopper-Pearson) two-sided 95% confidence interval will be constructed assuming an underlying binomial distribution for the ITT population via SAS:

```
proc freq data=dataset order=freq;  
  
    tables binary_outcome / binomial(exact) alpha=.05;  
  
run;
```

Failure to achieve the favorable outcome will be summarized in two sub-groups: the rate of patients having an HbA1c  $>$  6.5% at Day 365, and the rate of patients who experienced any SHE from Day 28 to Day 365.

The primary endpoint will be assessed for all treated patients from first transplant (including patients with  $>$ 1 transplant within 1 year of first exposure) and from last transplant. A patient's HbA1c results may be reported on visit days that do not fall on the exact Day 365. In this case the records from the date that is the closest to and within 4 weeks (28 days) before or after Day 365 will be used.

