#### **9.1.2. Treatment of Missing Data**

The primary endpoint should be evaluable for all patients in the ITT population. However missing data can occur due to death, if the patient withdraws consent to be followed, or if immunosuppression is begun but the patient never receives a transplant. In these cases the endpoint will be classified as failure to achieve a favorable outcome. Should the endpoint not be evaluated for a patient for other reasons, a failure will be imputed unless data available at a time longer than one year after transplant indicates otherwise, in which case, that later value will be imputed.

All imputations will be reported in a patient data listing along with the reasons for imputation. The rates and the exact 95% confidence intervals for complete data and imputed data will be compared to ascertain the sensitivity of the imputation.

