XXXXXXXXXX.sas, DDMMYYYY:HHMM

TABLE 14.1.5  
 Current Medical Conditions

Number (%) of Patients with Clinically Significant Current Medical Conditions

<PAGE 1 FORMAT>

Safety population (N=X)	Body System				
	Allergy n (%)	Immunology n (%)	Renal/Genitourinary n (%)	Cardio-vascular n (%)	Missing n (%)
	X (XX)	X (XX)	X (XX)	X (XX)	X (XX)

XXXXXXXXXXXX.sas, DDMMYYYY:HHMM

TABLE 14.1.6  
 Screening Physical Examination Results

	Body System					
	Number (%) of Patients with an Abnormality					
	Eyes	ENT	Respiratory	Gastro-intestinal	Genitourinary	Extremities
Safety population (N=X)	X/X (XX)	X/X (XX)	X/X (XX)	X/X (XX)	X/X (XX)	X/X (XX)
	Nervous System	Dermatologic	Lymph Nodes	Endocrine/Metabolic		
	X/X (XX)	X/X (XX)	X/X (XX)	X/X (XX)		

Note: The denominator is the number of patients that had the body system evaluated during the physical exam.

XXXXXXXXXX.sas, DDMMYYYY:HHMM

TABLE 14.1.7  
 Prior/Concomitant Medication Use at Baseline

Drug Class/ Preferred Drug Name	Islet Transplantation (N=X) n (%)
Subj. taking a prior/con. med.	X (XX)
Drug Class 1	
Preferred Name 1.1	X (XX)
Preferred Name 1.2	X (XX)
Preferred Name 1.3	X (XX)
etc.	
Missing	X (XX)

Note: Medications were coded using WHO Therapeutic drug classes and preferred names.

XXXXXXXXXX.sas, DDMMYYYY:HHMM

Table 14.1.8  
 Listing of Islet Infusions by Patients

Total # of Tx Received	Subj. No.	Seq. of Islet Infusion	Date of Islet Infusion
1 Tx	XXX	1	DDMMYYYY
	XXX etc.	1	DDMMYYYY
2 Tx's	XXX	1	DDMMYYYY
	etc.	2	DDMMYYYY
3 Tx's	XXX	1	DDMMYYYY
		2	DDMMYYYY
	etc.	3	DDMMYYYY

XXXXXXXXXX.sas, DDMMYYYY:HHMM

TABLE 14.2.1  
 Summary of Primary Efficacy Endpoint

ITT population (N=X)	Time of Evaluation Number (%) of Patients			
	1 Year after First Tx	(95% C.I.)	1 Year after Last Tx	(95% C.I.)
Success (HbA1c ≤ 6.5% + Free of SHE [1])	X (XX)	(XX, XX)	X (XX)	(XX, XX)
Failure Total	X (XX)		X (XX)	
HbA1c > 6.5%	X (XX)		X (XX)	
Any SHE [1]	X (XX)		X (XX)	
Missing [2]	X (XX)		X (XX)	

[1] SHE occurring between Day 28 and Day 365 (Day 0 being the day of corresponding transplant).

[2] Missing endpoints are imputed as failure.

XXXXXXXXXX.sas, DDMMYYYY:HHMM

TABLE 14.2.2a  
 Summary of Secondary Efficacy Endpoints:  
 Patients Attaining Insulin Independence at 1 Year after First and Last Transplant

ITT population (N=X)	Number (%) of Patients			
	First Tx Day 365		Last Tx Day 365	
	Missing	Missing	Missing	Missing
Absence of exogenous insulin	X (XX)	X (XX)	X (XX)	X (XX)

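### SAP 9.1.2 lets a value obtained after one year override an imputed failure without a rule for the hypoglycemia component, and the footnote to Table 14.2.1 omits that exception

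*SAP*

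**What the plan says.** SAP 9.1 defines the primary endpoint as a composite of two conditions. The first is HbA1c ≤ 6.5% at Day 365. The second is being "free of severe hypoglycemic events (for definition see Section 2.7.2a) from Day 28 to Day 365, inclusive". SAP 9.1.1 gives the HbA1c a visit window: the record "closest to and within 4 weeks (28 days) before or after Day 365 will be used".

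SAP 9.1.2 then sets the missing-data rules. For death, withdrawal of consent, or immunosuppression started without a transplant, "In these cases the endpoint will be classified as failure to achieve a favorable outcome". For any other reason, "a failure will be imputed unless data available at a time longer than one year after transplant indicates otherwise". Where such data exist, the later result takes the place of the failure. The section also promises a listing of all imputations with reasons, and a comparison of rates and exact intervals between complete and imputed data.

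The shell of the primary results table, Table 14.2.1, has a Missing row within the failure block. Its footnote reads "Missing endpoints are imputed as failure". Footnote [1] of the same table repeats the interval for the second component: "SHE occurring between Day 28 and Day 365 (Day 0 being the day of corresponding transplant". SAP 2.9, which lists changes from the protocol analysis, does not mention the later-value rule. SAP 9.2 carries the rule over to the categorical secondary endpoints.

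**The concern.** The HbA1c component is a measurement at a point in time, and a later measurement can arguably stand in for it. The SHE component is a condition on a closed interval in the past. A laboratory value drawn after the interval holds no record of what happened inside it. SAP 9.1.2 treats the composite as though it were one value that can be replaced. A programmer therefore has no instruction on how to judge the SHE component when the later value is favorable.

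The table footnote adds a second difficulty. Someone programming from the shell would score every missing endpoint as a failure. Someone programming from the text would score some of them as successes.

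What is at stake is the primary proportion and its exact interval. This is an open-label, single-arm trial meant to support a license application (SAP 2.1, 2.2), and SAP 9.1.1 makes estimating that proportion the primary analysis. Relative to the default of failure, the exception can only raise it.

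**Working it through.** **Inputs.** Expected success rate 80%; N=50 planned, and N=15 as the smallest size discussed (SAP 2.8). Exact (Clopper-Pearson) two-sided 95% intervals (SAP 9.1.1). The number of patients rescued by a later value is not in the documents, so the counts below are assumptions.

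**The plan's own precision figures.** The half-width is 1.96 × √(0.8 × 0.2 / n). For n=50 it is 0.1109 and for n=40 it is 0.1240, matching the stated 0.111 and 0.124. No figure in the plan is disputed.

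**The rules side by side.** Take a patient with no HbA1c within Day 365 ± 28, not covered by the three automatic-failure reasons, with a favorable value later on.

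- SAP 9.1.2: the later value is imputed and the patient can be a success.
- Table 14.2.1, footnote [2], read literally: failure.
- SHE component: SAP 9.1 and footnote [1] both require Days 28 to 365; SAP 9.1.2 does not say how this is established.

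**How far the exception reaches.** SAP 9.1.1 already admits an HbA1c up to Day 365 + 28 = Day 393. For HbA1c, the exception therefore operates only beyond Day 393, with no end date. Later values will often exist, because the 5-year and 10-year schedules (Protocol 6.6.9, 6.7.1) include HbA1c every three months. Protocol 6.5.1 allows further infusions during the 5-year follow-up. For the first-transplant endpoint, a late HbA1c may therefore reflect another graft.

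**Shift per patient.** 1/50 = 2.0 points; 1/15 = 6.7 points.

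**N=50, two rescued (assumed), 40 successes observed among the other 48:**

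| Handling | Result | Exact 95% CI |
|---|---|---|
| Complete data only | 40/48 = 83.3% | 69.8–92.5 |
| Imputed under SAP 9.1.2 | 42/50 = 84.0% | 70.9–92.8 |
| All missing = failure | 40/50 = 80.0% | 66.3–90.0 |

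The planned sensitivity comparison is the first row against the second, a difference of 0.7 points. The third row, 4 points below the second, is not called for.

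**N=15, one rescued (assumed):** 12/15 = 80.0% (51.9–95.7) with the later value; 11/15 = 73.3% (44.9–92.2) as a failure. The lower limit moves from above to below 50%, close to the improvement that SAP 2.8 calls minimally meaningful.

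**Limit at N=50.** If 40 successes under SAP 9.1.2 included five rescued patients (an illustrative bound, not a figure from the documents), failure-only would give 35/50 = 70.0% (55.4–82.1). The lower limit would still exceed 50%.

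**The case against.** The strongest reply is that the two rules need not conflict. The Missing row may hold only those patients still missing after SAP 9.1.2 has been applied, with the footnote as shorthand. That is a fair reading, but the footnote does not say so and needs a clarifying edit either way.

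A reader might also infer that the plan lets a single later HbA1c settle both components. The text does not support that. It speaks of data and a later value, never of HbA1c, and nothing in it waives the SHE condition. The defect is the absence of a component-wise rule.

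Nor does a missed one-year evaluation mean that the SHE history is lost. Home glucose logs, event review at every visit and serious-event reporting (Protocol 6.6.7, 6.9.5), and the episode records kept for the HYPO score (SAP 9.2), may cover the interval. If only the HbA1c is missing, a later one fills only that component and the objection is much narrower.

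It is also tempting to take the protocol's 10% attrition as the number of rescued patients. That would be wrong. The 10% is the allowance between 55 recruited and 50 studied, and withdrawn consent is already an automatic failure.

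Two further points stand. Missing-as-failure itself errs downward when a missing patient truly succeeded. The promised listing will also make each imputation visible. It does not supply the failure-only rate or interval, however.

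**Conclusion.** The concern holds in a limited form. SAP 9.1.2 lets a value from after one year replace an imputed failure on a composite without naming the component, bounding the time, or requiring documentation of the Day 28–365 SHE condition. Footnote [2], read literally, gives the same patient a different classification, and the planned sensitivity comparison leaves out the failure-only result.

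The size depends on an unknown count. At N=50 and about 80% success, a few rescued patients move the estimate by a few points and do not bring the lower limit near 50%. At N=15 one patient can carry it across 50%. That crossing is not a prespecified decision: the plan commits only to reporting the proportion and interval. The documents do not support calling the primary result invalid, or saying that SHE histories will in fact be unobserved. They do support settling the rule, since as written it can raise the primary rate without evidence on one of its two components.

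**What to change.** 1. In SAP 9.1.2, limit the later-value exception to the HbA1c component, with a stated maximum window after Day 365. Apply it only when freedom from SHE over Days 28 to 365 is documented; otherwise impute failure.
2. Reword footnote [2] of Table 14.2.1 to state that same rule.
3. Add a row to Table 14.2.1 counting successes that rest on a later HbA1c.
4. Report the rate with all missing endpoints counted as failures, with its exact 95% interval, as a named sensitivity result beside the complete-data comparison.

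Because SAP 9.2 borrows this rule, check that the revised wording still works for the categorical secondary endpoints. The cost is SAP wording and one table row, with no new data collection. The reported success rate may be slightly lower.

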## 9.2. Analysis of Secondary Endpoints

Except for the primary analyses there are no explicit or implied hypotheses in the protocol. Changes in the secondary outcomes are of interest as they will relate to efficacy as measured by the primary outcome variable. All the secondary endpoints will be evaluated at 1 year after the first and 1 year after the last transplant, respectively, with the day of corresponding transplant always designated Day 0.

We will evaluate the proportions of patients presenting with insulin independence among all patients and among the patients who fulfilled the primary endpoint, respectively. **Insulin independence** while fulfilling the primary endpoint will be further evaluated by the following parameters:

- Absence of exogenous insulin injection reported at Day 365.
- Fasting capillary glucose level not exceeding 140 mg/dL (7.8 mmol/L) more than three times in a week (based on measuring capillary glucose levels a minimum of 7 times in a seven day period) at Day 365 ± 28 days.
- Fasting plasma glucose level ≤ 126 mg/dL (7.0 mmol/L) at Day 365 ± 28 days (if the fasting plasma glucose level is > 126 mg/dL [7.0 mmol/L], it must be confirmed in an additional one out of two measurements).
- 2-hour postprandial capillary glucose not exceeding 180 mg/dl (10.0 mmol/L) more than one out of every seven times in a week (based on measuring capillary glucose levels a minimum of 7 times in a seven day period) at Day 365 ± 28 days.
- Evidence of endogenous insulin production defined as fasting or stimulated C-peptide levels ≥ 0.5 ng/mL (0.16 nmol/L) at Day 365 ± 28 days.

Number and percent (over the total number of patients attaining primary endpoint) of patients attaining each outcome listed above will be summarized.

**Hypoglycemic episodes** will be measured by the Ryan HYPO Score (Ryan et al., 2004) derived from the number and severity of hypoglycemic episodes recorded throughout the follow-up phase from Day 28 to Day 365. Additionally the percent reduction from baseline will be reported.

**Glucose variability and hypoglycemia duration will be measured by continuous glucose monitoring system (CGMS)** for a 3-day period at three different time points: 1) at screening, 2) one year after first islet transplant, and 3) one year after last islet transplant. The following measurements and analysis will be reported:

- Mean glucose concentration
- Percent of time in the following ranges:
  - < 60 mg/dl
  - 60-140 mg/dl
  - 141-200 mg/dl
  - > 200 mg/dl

As with the primary endpoint, the secondary endpoints should be available for all transplanted patients and the analyses will be conducted for the ITT population. If a categorical endpoint is not available for a patient, then it will be treated with the same missing data rules as used for the primary endpoint. If a scalar endpoint is not available for a patient within the designated time window around Day 365, a later value will be imputed if an evaluation is done at a time longer than one year after the final transplant, otherwise the patient will stay missing for the endpoint. If for any endpoints more than 50% of patients do not report data, the endpoints will then not be summarized.

All imputations and missing data will be reported in a patient data listing along with the reasons for imputation and/or missing data.

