6.10.2 Efficacy

Specification of Efficacy Parameters

a. Primary Efficacy Endpoint:

The proportion of subjects with an HbA1c \leq 6.5% and free of severe hypoglycemic events at 1 year after the first islet cell infusion

Standard insulin treatment can rarely improve glycemic control in brittle Type 1 diabetic patients who are already on state-of-the-art insulin therapy. In general these patients require insulin reduction to reduce hypoglycemic episodes, which would likely lead to higher HbA1c. In contrast, islet transplantation can reduce hypoglycemic episodes without increasing HbA1c.

Definition of severe hypoglycemic event: An event with symptoms compatible with hypoglycemia in which the subject required the assistance of another person and which was associated with either a blood glucose level < 50 mg/dl (2.8 mmol/L) or prompt recovery after oral carbohydrate, intravenous glucose, or glucagon administration.

For the primary endpoint (composite HbA1c \leq 6.5% and absence of severe hypoglycemic events), we expect 80% of the transplant population to achieve this endpoint. Therefore, assuming a sample size of 50, a two-sided 95.0% confidence interval for a single proportion will extend \pm 0.111 from the observed proportion. When the sample size is 40, a two-sided 95.0% confidence interval for a single proportion will extend \pm 0.124 from the observed proportion. Proportion and surrounding confidence interval will be reported.

Figure 2. Sample Size Curve for 95% Confidence Interval for Proportion

[figure not shown]
[figure not shown]

Figure 3 illustrates the cumulative percent of patients achieving HbA1c reduction from baseline in Phase1/2. As shown, all patients experienced a reduction in HbA1c (decrease of 0.6 to 2.7%). Furthermore, all patients presented with a HbA1c \leq 6.5 one year after final transplant.

Figure 3. Cumulative Percent of Patients Attaining HbA1c Reduction from Baseline at 1 Year after Last Transplant (N=7).

b. Secondary Efficacy Endpoints:

The secondary efficacy endpoints will focus on more detailed analysis of glycemic control, and will include the following:

1. **Insulin independence:** We will evaluate the proportion of subjects presenting with insulin independence while fulfilling the primary endpoint.

Definition of insulin-independence:

- Absence of exogenous insulin injection
- HbA1c \leq 6.5%

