#### **b. Secondary Efficacy Endpoint:**

The secondary efficacy endpoints will focus on more detailed analysis of glycemic control, and will include the following:

- 1) **Insulin independence:** We will evaluate the proportion of patients presenting with insulin independence while fulfilling the primary endpoint at 1 year after the first and 1 year after the last islet cell infusion, respectively.

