#### **Definition of insulin-independence:**

[figure not shown]
- Absence of exogenous insulin injection

- Fasting capillary glucose level should not exceed 140 mg/dL (7.8 mmol/L) more than three times in the past week based on measuring capillary glucose levels a minimum of 7 times in a seven day period.
  - Fasting plasma glucose level  $\leq$  126 mg/dL (7.0 mmol/L); if the fasting plasma glucose level is  $>$  126 mg/dL (7.0 mmol/L), it must be confirmed in an additional one out of two measurements.
  - 2-hour postprandial capillary glucose should not exceed 180 mg/dl (10.0 mmol/L) more than one out of every seven times in the past week based on measuring capillary glucose levels a minimum of 7 times in a seven day period (for the modification see Section 2.9 Changes from the Planned Protocol Analysis).
  - Evidence of endogenous insulin production defined as fasting or stimulated C-peptide levels  $\geq$  0.5 ng/mL (0.16 nmol/L)
- 2) **Hypoglycemic episodes** will be measured by the number and severity of hypoglycemic episodes quantified by the Ryan HYPO Score, and the percent reduction will be reported.
- 3) **Glucose variability and hypoglycemia duration will be measured by continuous glucose monitoring system (CGMS)** for a 3-day period at three different time points: 1) at screening, 2) one year after first islet transplant, and 3) one year after last islet transplant. The following measurements and analysis will be reported:
- Mean glucose concentration
  - Percent of time in the following ranges:
    - < 60 mg/dl
    - 60-140 mg/dl
    - 141-200 mg/dl
    - > 200 mg/dl

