Among patients fulfilling the primary efficacy outcome (N=X):				
Absence of exogenous insulin	X (XX)	X (XX)	X (XX)	X (XX)
Fasting capillary glucose in a week:				
Not exceeding 140 mg/dL more than 3X	X (XX)	X (XX)	X (XX)	X (XX)
Fasting plasma glucose $\leq$ 126 mg/dL	X (XX)	X (XX)	X (XX)	X (XX)
Postprandial capillary glucose in a week:				
Not exceeding 180 mg/dl more than 1X/7X	X (XX)	X (XX)	X (XX)	X (XX)
C-peptide (fasting or stimulated) $\geq$ 0.5 ng/mL	X (XX)	X (XX)	X (XX)	X (XX)

XXXXXXXXXX.sas, DDMMYYYY:HHMM

TABLE 14.2.2b  
 Summary of Secondary Efficacy Endpoints:  
 Patients' HYPO Score at 1 Year after First and Last Transplant

ITT population (N=X)		n	Mean	SD	Median	Minimum	Maximum	Missing n (%)
HYPO	Baseline (pre-Tx):	X	XX	XX	XX	XX	XX	X (XX)
	First Tx Day 365 % Reduction from baseline	X	XX	XX	XX	XX	XX	X (XX)
	Last Tx Day 365 % Reduction from baseline	X	XX	XX	XX	XX	XX	X (XX)

XXXXXXXXXXXX.sas, DDMMYYYY:HHMM

TABLE 14.2.2c  
 Summary of Secondary Efficacy Endpoints:

Patients' Glucose Variability and Hypoglycemia Duration at 1 Year after First and Last Transplant

ITT population (N=X)		n	Mean	SD	Median	Minimum	Maximum	Missing n (%)
Baseline	Mean Glucose	X	XX	XX	XX	XX	XX	X (XX)
	Percent time in range:							
	< 60 mg/dl	X	XX	XX	XX	XX	XX	X (XX)
	60-140 mg/dl	X	XX	XX	XX	XX	XX	X (XX)
	141-200 mg/dl	X	XX	XX	XX	XX	XX	X (XX)
	> 200 mg/dl	X	XX	XX	XX	XX	XX	X (XX)
First Tx Day 365	Mean Glucose	X	XX	XX	XX	XX	XX	X (XX)
	Percent time in range:							
	< 60 mg/dl	X	XX	XX	XX	XX	XX	X (XX)
	60-140 mg/dl	X	XX	XX	XX	XX	XX	X (XX)
	141-200 mg/dl	X	XX	XX	XX	XX	XX	X (XX)
	> 200 mg/dl	X	XX	XX	XX	XX	XX	X (XX)
Last Tx Day 365	Mean Glucose	X	XX	XX	XX	XX	XX	X (XX)
	Percent time in range:							
	< 60 mg/dl	X	XX	XX	XX	XX	XX	X (XX)
	60-140 mg/dl	X	XX	XX	XX	XX	XX	X (XX)
	141-200 mg/dl	X	XX	XX	XX	XX	XX	X (XX)
	> 200 mg/dl	X	XX	XX	XX	XX	XX	X (XX)

Note: Baseline levels were measured prior to the initial transplant.

XXXXXXXXXX.sas, DDMMYYYY:HHMM

TABLE 14.3.1  
 Overall Summary of Treatment-Emergent Adverse Events

Type of AE	# of Islet Transplantations Received			
	Total [1] (N=X)	1 Tx (N=X)	2 Tx's (N=X)	3 Tx's (N=X)
TEAEs				
Events	X	X	X	X
Patients: n(%)	X (XX%)	X (XX%)	X (XX%)	X (XX%)
Serious TEAEs				
Events	X	X	X	X
Patients: n(%)	X (XX%)	X (XX%)	X (XX%)	X (XX%)
TEAEs leading to discontinuation				
Events	X	X	X	X
Patients: n(%)	X (XX%)	X (XX%)	X (XX%)	X (XX%)
TEAEs with an outcome of death				
Events	X	X	X	X
Patients: n(%)	X (XX%)	X (XX%)	X (XX%)	X (XX%)

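### SAP 9.2 promises an insulin-independence proportion in all patients, but Table 14.2.2a has no row for the joint endpoint

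*SAP*

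**What the plan says.** Protocol 6.10.2 lists insulin independence as the first secondary efficacy endpoint. SAP 2.7.2b keeps it, for one year after the first and one year after the last infusion: "We will evaluate the proportion of patients presenting with insulin independence while fulfilling the primary endpoint". Both documents treat insulin independence as one definition with several parts: no injected insulin, limits on fasting capillary glucose, fasting plasma glucose and postprandial glucose, and evidence of C-peptide. (The protocol's list also has an HbA1c limit. The SAP's list has a lost figure at that place, so nothing is made of the difference, and the primary endpoint carries the same limit.)

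SAP 9.2 first makes a promise about denominators: "We will evaluate the proportions of patients presenting with insulin independence among all patients and among the patients who fulfilled the primary endpoint, respectively". It then lists the five criteria and says: "Number and percent (over the total number of patients attaining primary endpoint) of patients attaining each outcome listed above will be summarized". Further on it says of the secondary endpoints that "the analyses will be conducted for the ITT population".

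Shell 14.2.2a has a title that announces insulin independence. It contains one row on the ITT denominator, for being off exogenous insulin. A block follows whose heading begins "Among patients fulfilling the primary efficacy outcome (N=X", with one row for each of the five criteria. Listing 16.2.6b shows insulin independence patient by patient, for the first transplant only.

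**The concern.** A programmer who follows the shell will produce no estimate of the defined endpoint, either over ITT or over responders. What appears under its name is a looser quantity (off insulin) and five separate criteria in a selected subgroup. Section 2.9, which records departures from the protocol's analysis, mentions the relaxed postprandial rule and the added time point, but not this substitution.

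The trial is meant to support a license application. A reader who takes the table at its title would attribute to insulin independence a rate that belongs to something easier to reach.

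**Working it through.** The documents state no rate, sample size or power for insulin independence, so there is no planned figure to reproduce. The check has two parts.

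**What is promised against what is tabulated**

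| Quantity | Text | Shell 14.2.2a |
|---|---|---|
| All criteria and primary endpoint met, over ITT | Endpoint in Protocol 6.10.2 and SAP 2.7.2b; all-patient proportion in SAP 9.2 | No row |
| All criteria met, among responders | Second proportion in SAP 9.2 | No row |
| Off insulin only, over ITT | First criterion only | One row |
| Each criterion separately, among responders | Operational sentence in SAP 9.2 | Five rows |

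**How the planned rows relate to the joint rate**

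Let N be the ITT size, R the number of responders, x the number of responders meeting a given criterion, and J the number meeting all five criteria and the primary endpoint.

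- J cannot exceed x, and R cannot exceed N. So J/N ≤ x/R for every responder row.
- Everyone counted in J is off insulin. So J/N is at most the ITT off-insulin rate, which also counts patients who fail on HbA1c, severe hypoglycemia, glucose or C-peptide.
- With five criteria each met by x responders, J lies between max(0, 5x − 4R) and x. If the criteria were independent among responders, J would be about R(x/R)^5.

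These inequalities need the same missing-data rule for the components and the joint outcome.

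**Illustration**

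Inputs from SAP 2.8: N = 50 and an expected primary rate of 80%, so R = 0.80 × 50 = 40. The criterion rates are assumptions, since the documents give none; a range of 70% to 95% is shown.

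| x of 40 (assumed) | Each responder row shows | Range of J | J/50 | J/50 if independent |
|---|---|---|---|---|
| 38 | 95% | 30 to 38 | 60% to 76% | 62% |
| 36 | 90% | 20 to 36 | 40% to 72% | 47% |
| 32 | 80% | 0 to 32 | 0% to 64% | 26% |
| 28 | 70% | 0 to 28 | 0% to 56% | 13% |

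For x = 36: the lower limit is 5 × 36 − 4 × 40 = 20, and 20/50 = 40%. The upper limit is 36/50 = 72%. Under independence, 40 × 0.9^5 = 23.6, and 23.6/50 = 47%.

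The denominator alone makes any count look 50/40 = 1.25 times larger. A reader can undo that from the printed counts. The overlap between criteria cannot be recovered from the rows.

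**The case against.** The strongest reply is that SAP 9.2 does plan the proportion. It names all patients as a denominator, SAP 2.7.2b supplies the full definition, and the component summary is introduced as a further evaluation, which reads as an addition and not a replacement. This stands against one inference a reader might draw, that the sponsor never intends to compute the joint endpoint in all patients. The text promises it, and listing 16.2.6b shows individual status. But SAP Section 12 says the shells carry the statistics each table needs, and this shell has no such row. The listing gives no proportion and omits the last transplant.

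Second, the planned rows are labelled as components with their denominators and missing counts, so no row claims to be the joint endpoint. That also stands. The risk of misreading comes from the table title and the absent row.

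Third, the size is hypothetical. The lower limits require failures on different criteria to fall in different patients as far as possible, and independence is doubtful when three of the five criteria are glucose measures in the same people. The ranges show what the table cannot tell, not what will happen.

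Fourth, a joint row is exposed to diary gaps. SAP 2.9 expects frequent missing postprandial data, so counting missing as failure could understate insulin independence. This is a fair constraint on the remedy, and the fix takes account of it.

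**Conclusion.** The mismatch between text and shell is real. SAP 9.2 promises insulin independence in all patients and in responders, the endpoint is defined jointly, and no planned summary row reports it for either denominator or either time point.

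The direction is certain under a consistent missing-data rule: each planned row equals or exceeds the joint ITT rate. A reader might go further and conclude that the table will overstate insulin independence by a known or large amount. The documents do not support that, because they give no criterion rates and the gap can be small if the criteria largely coincide and nearly all patients are responders. With the SAP's N of 50 and 80% responders, and an assumed 36 of 40 on each criterion, rows showing 90% are compatible with a joint ITT rate anywhere from 40% to 72%.

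This should be corrected before the table is programmed. It concerns a secondary endpoint without a hypothesis test, but a named endpoint would otherwise have no estimate.

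**What to change.** Add to Table 14.2.2a, separately for the first and last transplant, one row for patients who meet all insulin-independence criteria and the primary endpoint, as n/N over the full ITT population.

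- Use the rule that SAP 9.2 already carries over from 9.1.2: failure, unless data later than one year indicate otherwise.
- Beside the row, show how many patients are classed as failures because of missing data.
- Say how the 9.2 rule against summarizing endpoints with more than 50% of patients not reporting applies to the joint row.
- Preferably add an exact 95% confidence interval, as for the primary endpoint. The SAP does not require intervals for secondary endpoints, so this is a recommendation.
- Label the existing ITT row as absence of insulin only, and keep the component rows as description.

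The cost is one derived variable, one row per time point and a missing count. The reported rate may be lower than the rows now planned, and incomplete diaries may pull it down further. The missing count makes that visible.
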